8.3.1 Overall Comfort

When the sample size in each group is 300 eyes (150 subjects), a two-group one-sided 0.025 significance level t-test will have 99% power to reject the null hypothesis that the test is not non-inferior to the standard (the difference in means, μ T- μ S, is -5 or farther from zero in the same direction) in favor of the alternative hypothesis that the Test is non-inferior, assuming that the expected difference in means is 0 and the common standard deviation is 13.264.

8.3.2 Vision

When the sample size in each group is 300 eyes (150 subjects), a two-group one-sided 0.025 significance level t-test will have 99% power to reject the null hypothesis that the test is not non-inferior to the standard (the difference in means, μ T- μ S, is -5 or farther from zero in the same direction) in favor of the alternative hypothesis that the non-inferior, assuming that the expected difference in means is 0 and the common standard deviation is 11.7.

8.3.3 Front Surface Deposits

With 300 eyes (150 subjects) in each group, the observed one-sided 97.5% confidence interval will be expected to exceed -0.1 with 99% power when the Standard proportion, π_0 , is 0.942 and the Test expected proportion, π_1 , is 0.942; results are based on 100,000 simulations using the Newcombe-Wilson score⁶ method to construct the confidence interval.⁶

8.3.4 Slit-Lamp Findings Greater than Grade 2

With 300 eyes (150 subjects) in each group, the observed one-sided 97.5% confidence interval will be expected to be less than 0.05 with 99% power when the Standard proportion, π_0 , is 0.008 and the Test expected proportion, π_1 , is 0.008; results are based on 100,000 simulations using the Newcombe-Wilson score method to construct the confidence interval.

8.3.5 Lens Groups

For each lens group in Table , at least approximately 30 test group subjects will complete the study. For a sample size of 30, the probability of observing at least one complication will be at least 95% when the true complication rate is 10% or greater.

8.3.6 Overall Power

If the four primary endpoints are independent, then the overall power of the study is 99% x 99% x 99% x 99% = 96%.

8.3.7 Enrollment Targets

Approximately 300 subjects (150 in each treatment group) will complete the trial. Allowing for up to 10% losses and for equal enrollment across sites, the enrollment target will be approximately 340 subjects (680 eyes).

To allow for approximately 30 completed test group subjects per lens group, each lens group will enroll approximately 34 test group subjects.

8.4 Randomization

An unmasked statistician who is not otherwise involved in the trial will create the randomization schedule.

Each subject will be randomized to one of the treatment arms in a 1:1 ratio (Test to Control). Randomization will be managed using a RTSM system. The randomization will be stratified by lens group and investigational site.

Efforts will be made to enroll subjects in at least three of the lens strata within each site to minimize confounding between site and lens group. While the target enrollment for each lens group is approximately 68 subjects, some lens strata may be difficult to enroll.

8.5 Study Populations

8.5.1 Intent-to-Treat (ITT) Population

The ITT Population will consist of all randomized subjects for subject level summaries and, for eye level summaries, both of their eyes. Subjects will be included in ITT Population summaries according to the treatment group to which they were randomly assigned.

8.5.2 Per Protocol (PP) Population

The PP Population will consist of all ITT Population subjects without important (major) protocol deviations for subject level summaries and, for eye level summaries, both of their eyes. Important protocol deviation categories are defined in Section 8.6.5 below. Subjects will be included in PP Population summaries according to the treatment group to which they were randomly assigned. The membership of the PP population will be determined prior to unmasking.

8.5.3 Safety Population

The Safety Population will consist of all dispensed subjects and, for eye level summaries, both of their eyes. Subjects will be included in Safety summaries according to the treatment that they received. If a subject receives more than one treatment and one of those treatments is the Test solution, then the subject will be included in Safety Population summaries under the Test treatment group.

8.6 Statistical Analysis

8.6.1 Methods of Analysis

8.6.1.1 General Methods

Continuous data will be summarized using sample size (n), mean, standard deviation (SD), median, minimum, and maximum. Categorical data will be presented using the total counts for each category and corresponding percentages. The denominator for each percentage will be the number of subjects or eyes with non-missing data unless otherwise indicated.

As is customary for contact lens solution trials, eyes will be treated as independent sampling units in eye level analyses unless otherwise noted.

Listings of data will be produced in addition to tables of summary statistics.

8.6.1.2 **Overall Comfort**

At each follow-up visit, overall comfort will be assessed for each eye on a scale from 0 to 100, with 100 denoting the most favorable response. For each eye, mean overall comfort over all follow-up visits will be computed as the average of the non-missing values over all scheduled follow-up visits. Missing data will not be imputed for the primary analysis. Mean overall comfort over all follow-up visits will be summarized at the eye level by treatment using continuous summary statistics for the ITT Set in a table. A one-sided lower 97.5% confidence limit around the difference in means between the Test and Control treatment groups, computed using an analysis of variance model including the fixed factors of treatment, site, and lens group will be displayed. If the lower confidence limit is greater than -5.0, then the null hypothesis that the test solution is not noninferior will be rejected, and the test solution will be statistically successful in this outcome.

As a sensitivity analysis, the PP Population will be analyzed for this endpoint.

8.6.1.3 Vision

At each follow-up visit, vision will be assessed for each eye on a scale from 0 to 100, with 100 denoting the most favorable response. Vision will be analyzed using the methods described above for overall comfort.

8.6.1.4 Front Surface Deposits

At each follow-up visit, the degree of front surface deposits will be graded for each eye as 0, 1, 2, 3, or 4. Using only the non-missing observations from scheduled follow-up visits without imputation, each eye will be classified with respect to the maximum grade of front surface deposits (≤ 2 , > 2) observed over all follow-up visits. Maximum Front Surface Deposits Over All Follow-up Visits (≤ 2 , > 2) will be summarized at the eye level by treatment using categorical summary statistics for the ITT Set in a table. A one-sided lower 97.5% confidence limit around the difference in " ≤ 2 " proportions between the Test and Control treatment groups will be constructed using the Newcombe-Wilson score method. If the lower confidence limit is greater than -10.0% or if no deposits with grade greater than 2 are observed in either treatment group, then the null hypothesis that the Test solution is not noninferior will be rejected, and the Test solution will be statistically successful in this outcome.

As a sensitivity analysis, the PP Population will be analyzed for this endpoint.

8.6.1.5 Graded Slit-Lamp Findings > Grade 2

At each follow-up visit, graded slit-lamp findings will be assessed for each eye using Grades 0 through 4. Using only the non-missing observations from all visits, each eye will be classified with respect to findings greater than grade 2 at any visit (Absent, Present). Greater than grade 2 findings (Absent, Present) will be summarized at the eye level by treatment using categorical summary statistics for the Safety Set in a table. A one-sided upper 97.5% confidence limit around the difference in "Present" proportions between the Test and Control treatment groups will be constructed using the Newcombe-Wilson score method. If the upper confidence limit is less than 5.0% or if no findings greater than grade 2 are observed in either treatment group, then the null hypothesis that the Test solution is not noninferior will be rejected, and the Test solution will be statistically successful in this outcome.

8.6.1.6 **Subject Assessment**

At the Exit visit, subjects will report their level of agreement with each of a series of twelve statements in the Subject Assessment Questionnaire. Responses will be on a scale of one (strongly disagree) through six (strongly agree). These values will be dichotomized for analysis, with responses of one through three being mapped to the category of "Disagree" and responses of four through six being mapped to "Agree."

Statistical testing will proceed in two hierarchical families of twelve statistical tests each (one test per statement), with the null hypotheses of the first family eligible for rejection if all the primary endpoints are met.

The first family will employ a one-sided exact binomial test to compare the proportion of respondents in the Test group agreeing with each statement to 0.5.

The second family will employ a one-sided chi-square test to compare the proportion of respondents agreeing with each statement between the treatment groups.

Within each family of hypothesis tests, the *P*-values will be adjusted for multiplicity using the Holm method. Adjusted one-sided *P*-values less than 0.025 will show statistical significance.

The responses to each statement will be summarized categorically (1, 2, 3, 4, 5, 6, Agree, Disagree) by treatment group in a table for the ITT Set. The adjusted *P*-values from the statistical tests will also be displayed along with an indicator of statistical significance. If the statistical tests in a family are not eligible for rejection due to hierarchy, then the adjusted *P*-values for that family will not be displayed.

8.6.2 Adverse Events

All AEs occurring during the study will be recorded and classified on the basis of Medical Dictionary for Regulatory Activities (MedDRA) terminology. Descriptions of AEs will include the date of onset, the date the AE ended, the severity of the AE, the relationship to the study device, the action taken regarding study medication usage, the action taken to treat the AE, and the outcome. All reported treatment-emergent AEs (TEAEs) will be summarized by the number of subjects reporting AEs, system organ class, severity, seriousness, and relationship to study device. TEAEs are those AEs with an onset on or after the date of the first study device use.

Adverse events will be summarized by treatment group and severity. Each subject will be counted only once within a system organ class or a preferred term by using the AEs with the highest severity within each category.

Adverse events will be summarized by treatment group and relationship to study medication. Each subject will be counted only once within a system organ class or a preferred term by using the AEs with the greatest relationship within each category.

All information pertaining to AEs noted during the study will be listed by subject, detailing verbatim given the Investigator, preferred term, system organ class, start date, stop date, severity, action taken, and device relatedness. The AE onset will also be shown relative (in number of days) to the day of initial use of the randomized study device.

Serious adverse events (SAEs) will be tabulated by subject within treatment groups.

In addition, a list of subjects who discontinued from the study and a list of subjects who experienced SAEs will also be provided.

8.6.3 Subject Demographics and Baseline Characteristics

Demographics and baseline characteristics will be summarized descriptively by treatment and overall, for the ITT, PP, and Safety Populations.

8.6.4 Subject Discontinuation

The reasons for study discontinuation will be summarized by treatment and overall, for the ITT Population.

8.6.5 **Protocol Deviations**

Important (major) protocol deviations will be summarized by category and treatment group for the ITT Population in a table.

Categories of important protocol deviations will include the following.

- Ineligibility at screening/dispensing but randomized
- Not dispensed study treatment
- Misrandomization
- Dispensing of the incorrect solution
- Dispensing and use of lenses from the incorrect lens group
- Use of medications that could potentially affect any of the primary effectiveness endpoints
- Failure to comply with the procedures used to assess the primary effectiveness endpoints, such as missing the scheduled visit or failing to complete the procedure in accordance with instructions

Additional important protocol deviation categories may be added prior to unmasking.

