3.1 Description of Study Design

The study is designed to examine whether BL-3100-NBR03 multi-purpose solution cleaning and disinfecting solution is non-inferior to renu® Advanced Formula multi-purpose solution in several primary endpoints.

Approximately 340 subjects (680 eyes) will be enrolled in this three-month multicenter, randomized, double-masked, parallel-group, bilateral study at approximately 22 investigative sites in the United States (US). Approximately one-half (50%) of the eligible subjects will be randomized to receive Bausch + Lomb investigational BL-3100-NBR03 multi-purpose solution (Test), and approximately one-half (50%) of the eligible subjects will be randomized to receive renu® Advanced Formula multi-purpose solution (Control). In addition, all subjects will be dispensed three new pairs (including two back-up pairs) of their habitual lenses at the beginning of the study for daily wear, and scheduled replacement lenses at the 1-Month and 2-Month Follow-up Visits.

All subjects will be seen for a Screening/Dispensing Visit, at which the informed consent form (ICF), including the Health Insurance Portability Accountability Act (HIPAA), will be obtained and eligibility will be assessed. If eligible, subjects will be dispensed three new pairs of their habitual lenses and a Study Kit containing a cleaning and disinfecting solution according to the subject's randomly assigned treatment. Subjects may also be dispensed a supply of *Bausch* + *Lomb renu*® *Contact Lens Moisture Drops* to be used on an as needed basis. Subjects must NOT use ANY other cleaning and disinfecting solution or rewetting drops during the study.

Subjects are to wear their study lenses on a daily wear basis and are to use the Test or Control multi-purpose solution and care regimen after removing the lenses each day. Subjects will return their worn lenses to the unmasked designee at each monthly follow-up visit and will return their used and unused study solutions to the unmasked designee at the three-month follow-up visit (or early study termination/suspension visit) for return to the Sponsor.

Eligible subjects will be enrolled into one of five lens groups based on their habitual contact lenses. Subjects will be randomized to receive either the Test or Control multi-purpose

Study #914 - Protocol

solution. The five lens groups will be comprised of habitual wearers of soft lenses based on lens material as indicated in the table below.

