6.2.2 Early Study Termination/Suspension

If during the study it becomes evident to the Sponsor that the study should be stopped prematurely or placed on hold, appropriate notification will be given to the Investigator(s), IRBs, and FDA, as applicable. Bausch + Lomb will instruct the Investigators to stop/restart dispensing study materials and will arrange for study closeout, if applicable, at each site.

6.3 **Concomitant Medications/Therapy**

Study subjects are not allowed to use other lens care products, ocular solutions, ocular medications, or eye drops (over-the-counter or prescription) during the study unless specifically approved by the Investigator following consultation with the Sponsor. Use of other contact lenses is not allowed.

Ocular medications, systemic or topical medications that, in the Investigator's opinion, could potentially affect ocular physiology or lens performance are also prohibited, unless medically necessary during the course of the study. If used during the course of the study, these medications must be recorded in the appropriate eCRF.

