**Table 4 Study Populations**

Subject Study Population	Description
Intent-to-Treat (ITT) Population	The ITT Population will consist of all randomized subjects for subject level summaries and, for eye level summaries, both of their eyes. Subjects will be included in ITT Population summaries according to the treatment group to which they were randomly assigned.
Per Protocol (PP) Population	The PP Population will consist of all ITT Population subjects without important (major) protocol deviations for subject level summaries and, for eye level summaries, both of their eyes. Subjects will be included in PP Population summaries according to the treatment group to which they were randomly assigned. The membership of the PP population will be determined prior to unmasking.
Safety Population	The Safety Population will consist of all dispensed subjects and, for eye level summaries, both of their eyes. Subjects will be included in Safety Population summaries according to the treatment that they received. If a subject receives more than one treatment and one of those treatments is the Test solution, then the subject will be included in Safety Population summaries under the Test treatment group.

The Safety Population is used to analyze the endpoints and assessments related to safety. The ITT Population is used to analyze endpoints related to the primary efficacy objectives and all other non-safety summaries (unless noted otherwise). The PP Population is used for a sensitivity analysis of the primary efficacy endpoints.

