### **4.2.1. Protocol Deviations**

In the event a protocol deviation occurs, the date of and reason for deviations must be documented in all cases. Significant or major protocol deviations impacting the rights or safety of the subject or the integrity of the study must be reported by the Investigator to the IRB/EC and Medical Monitor immediately. Reporting of all other protocol deviations must adhere to the requirements of the governing IRB/EC. Unless the protocol deviations put the subject at risk or the subject's condition requires that they be discontinued from the study, subjects may continue to participate until the end of the study.

Major protocol deviations will be summarized by subject. All protocol deviations will be provided in a corresponding listing.

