#### 4.5.3. Sensitivity Analyses

The four primary endpoints ( $>$ Grade 2 slit-lamp findings, overall comfort, vision, and front surface deposits) will each have the following sensitivity analyses performed:

- **PP Analysis:** the original analyses will be repeated using the PP Population (efficacy endpoints only: overall comfort, vision, and front surface deposits).
- **Best/Worst-Case Imputation Analysis:** each eye with missing values at any scheduled follow-up visit will have their missing values imputed and analyzed twice (analyzed repeating the original analysis using the ITT Population), once using the best- and once using the worst-case scenarios. Following Yan et al. (2009), the worst-case imputation imputes the worst response observed among the test group for the missing responses in the test group, and imputes the best response observed in the control group for the missing responses in control group. The best-case imputation is the reverse of this: impute the best response observed among the test group for the missing responses in the test group, and impute the worst response observed in the control group for the missing responses in control group.

For slit-lamp findings, the best response is "Absent" (i.e. no findings  $>$ Grade 2), and worst is "Present". For overall comfort / vision, the best response is the equivalent to the largest response, and worst is equivalent to the smallest response (scale of 0-100). For

frontal surface deposits, the best response is no grade greater than 2, while the worst is a grade of 2 or greater.

- **Tipping-point Analysis:** If any observed-cases primary efficacy analysis conclusion is different than either the best-case or worst-case imputation conclusion (i.e. the observed-cases primary efficacy analysis concludes non-inferiority, but the worst-case imputation fails to conclude non-inferiority), then an additional tipping-point analysis will be performed for that endpoint using the ITT Population.

The tipping-point analysis will follow the spirit of the algorithms for continuous and binary data, as appropriate, as described in Yan et al. (2009).

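### Must the per-protocol rules name use of a non-study solution, or low use of the assigned one, for the PP analysis to do its job?

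*Protocol*

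**What the plan says.** Protocol 8.5.2 defines PP by exclusion and points onward: "Important protocol deviation categories are defined in Section 8.6.5 below". SAP Table 4 keeps the definition ("The PP Population will consist of all ITT Population subjects without important (major) protocol deviations for subject level summaries") and adds no list, so Protocol 8.6.5 holds the only one.

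That section opens its list with "Categories of important protocol deviations will include the following". Its seven entries are, in short: ineligible but randomized; not dispensed; misrandomized; wrong solution dispensed; lenses from the wrong group dispensed and used; medications that could affect the effectiveness endpoints; and non-compliance with the endpoint assessments, including missed visits. The section ends: "Additional important protocol deviation categories may be added prior to unmasking".

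On other products, Protocol 3.1 says "Subjects must NOT use ANY other cleaning and disinfecting solution or rewetting drops during the study", and 6.3 says "Study subjects are not allowed to use other lens care products, ocular solutions, ocular medications, or eye drops", the latter with an exception for use approved by the investigator after consulting the sponsor. On severity, SAP 4.2.1, repeating Protocol 6.5, says "Significant or major protocol deviations impacting the rights or safety of the subject or the integrity of the study must be reported".

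SAP 4.5.3 limits the role of PP: "the original analyses will be repeated using the PP Population (efficacy endpoints only: overall comfort, vision, and front surface deposits"). An item on whether the subject used the solution and wore the lenses on at least 80% of days is recorded at the 3-Month visit (Protocol 6.1.4) and tabulated (SAP 4.9, Lens Wear Parameters). No primary-endpoint analysis uses it.

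**The concern.** The test article is a solution, yet the entries that concern the solution cover only allocation and dispensing. For lenses the list mentions use; for the solution it does not. The nearest entries do not reach the point: one is about medications, which Protocol 6.3 lists separately from lens care products, and the other is about assessment procedures, not daily lens care. Read literally, a subject who was given the right bottle and used another product, or seldom used the assigned one, stays in PP.

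Non-inferiority is where this could matter. If such subjects have outcomes like those of the other arm, the difference shrinks and a poorer product can look acceptable. ITT keeps them by design, so a reader would look to PP for reassurance. The 80% item is collected but does not enter any comparison, and Protocol 6.4 says compliance will be assessed while Protocol 8.6.6 and SAP 4.4.2 say it will not be summarized. What is at stake is how informative a supportive analysis can be.

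**Working it through.** **1. The plan's own figure.** Protocol 8.3.1 takes 300 eyes per arm, SD 13.264, margin 5, true difference 0 and one-sided alpha 0.025, and states 99% power for comfort. SE = 13.264 × √(2/300) = 1.083. The noncentral t gives 99.6%, so the stated figure holds under the plan's assumption of independent eyes.

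**2. What dilution could do.** Let f be the share of Test subjects with Control-like outcomes. The documents give no value, so 10% and 20% are assumptions. Suppose the true difference among the remaining subjects is exactly at the margin. The all-randomized difference is then −5(1 − f) for comfort and vision, and the chance of passing is Φ(5f/SE − 1.96). For vision, SE = 11.7 × √(2/300) = 0.955. For deposits, Control is 0.942 and Test is 0.842 + 0.1f, with exact binomial enumeration of the Newcombe-Wilson lower limit against −0.10.

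| Endpoint | f | All-randomized difference | Chance of passing, 300 per arm | 150 per arm (fellow eyes fully correlated) |
|---|---|---|---|---|
| Comfort | 10% | −4.5 | 6.7% | 5.1% |
| Comfort | 20% | −4.0 | 15.0% | 9.6% |
| Vision | 10% | −4.5 | 7.5% | 5.6% |
| Vision | 20% | −4.0 | 18.1% | 11.1% |
| Deposits | 10% | −9% | 6.0% | 4.6% |
| Deposits | 20% | −8% | 12.7% | 8.1% |

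**3. What these figures do and do not show.** They are not error rates of the planned test. SAP Table 2 defines the estimand over all randomized eyes, and on that scale every difference in the table is inside its margin (−4.5 > −5; −9% > −10%), so passing is a correct decision. They would be errors only if the margin applied to users alone, which the plan does not say. Nor do they compare PP with and without the subjects in question. The direction is also assumed: a third product, or skipped cleaning, need not produce Control-like outcomes and could move the difference either way.

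**4. Whether the plan can exclude such subjects.** It can. The list may be extended until unmasking, PP membership is settled before unmasking (Protocol 8.5.2, SAP Table 4), and Protocol 6.5 and SAP 4.2.1 treat threats to study integrity as major. Some low users are already covered: a subject who stops, leaves and misses visits falls under the assessment entry. PP as listed also deals with other subject behaviour, through medication use, use of wrong-group lenses and missed visits. Only solution use is unnamed.

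**5. Whether the 80% item would improve matters.** Precision is not the obstacle with independent eyes: with 10% or 20% of each arm removed (270 or 240 eyes), comfort power is 99.2% or 98.5%, and the half-width goes from 2.13 to 2.24 or 2.38 points. The difficulty is what the item measures. It combines solution use with lens wear, so it would drop someone who used the solution on every wearing day but wore lenses less often. It cannot detect another product. It is absent from the Exit Visit steps (Protocol 6.1.5), so early leavers have no value. Appendix C tells subjects to stop use if irritation persists, so low use may be a consequence of the solution, and restricting to high users could favour Test.

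**6. Compliance wording.** Protocol 6.4 relies on lens wear data, and SAP 4.9 tabulates those data, including the 80% item. Protocol 8.6.6 and SAP 4.4.2 rule out a separate compliance summary. The wording pulls in two directions, but the data are reported.

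**The case for a change.** The best reply is that permission is not prespecification. An open list and a phrase about study integrity leave classification to case-by-case judgement, SAP V2 added no category, and SAP 4.10 declares no change on this point. The prohibition in Protocol 3.1 is emphatic, and naming the breach would take one line before unmasking.

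The literal reading stands, and such a line would do no harm if the cases were identified by masked staff from deviation and concomitant product records. Returned bottles would not serve: they show what happened to the study solution, not what else was used. They are also handled by unmasked designees, and the Clinical Monitor becomes unmasked at reconciliation, before database lock (Protocol 4.6).

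The reply does not establish a need. The judgement it distrusts is made before unmasking, so it cannot be guided by treatment results. Some judgement would remain even with a named category, because Protocol 6.3 allows approved exceptions. And no decision in the trial turns on PP.

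**Conclusion.** No change follows. The omission is real as a matter of wording, but it is a gap that a masked deviation review fills sensibly under the plan as written. It touches one supportive analysis of three endpoints; the ITT and Safety decisions, the four-endpoint success rule and the sample size are unaffected. Its numerical effect on PP cannot be estimated, because the documents give no rate of non-use. The illustrative pass probabilities of 4.6% to 18.1% rest on an assumed f of 10% or 20%, on Control-like outcomes in those subjects, and on a margin applied to users; under the plan's own estimand they are not wrong decisions. An added comparison in subjects at 80% or more is a debatable trade-off with no clear gain, since it selects after randomization and could favour Test. This conclusion assumes that the deviation review takes place before unmasking, as both documents require.
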